#### 8.8.3 Completion of the study

Upon completion of the 6 months off study assessments subjects will have completed study participation and be taken off study.

## 9. DATA AND SAFETY MONITORING PLAN

### 9.1 Safety Monitoring

**Principal Investigator:** Accrual, efficacy and safety data will be monitored by [name]., the Principal Investigator.

**NIH Intramural IRB.** Prior to implementation of this study, the protocol and the proposed subject consent and assent forms will be reviewed and approved by the properly constituted Institutional Review Board (IRB) operating according to Title 45 CFR 46. This committee will also approve all amendments to the protocol or informed consent, and conduct continuing annual review so long as the protocol is open to accrual or follow up of subjects, or data analysis continues.

**NHLBI DSMB:** The NHLBI Data Safety and Monitoring Board will review the protocol at an interval to be determined by the DSMB. A progress report will be forwarded to the DSMB at these times and their recommendations will be expeditiously implemented. The DSMB may recommend early termination of the study for considerations of safety and efficacy.

### 9.2 Adverse Events

Because dexamethasone is an FDA approved drug with known toxicity profile, any observed or volunteered adverse events will not be captured in the database unless (1) the adverse event is previously unknown (not on the label) or more severe than on the label and deemed possibly, probably or definitely related to the study medication or (2) meets the criteria for a severe adverse event. Adverse events that are complications of the primary transplant protocol and deemed unlikely or unrelated to dexamethasone will not be captured in the database for this protocol, but will be collected and reported in the transplant protocol. The collection of AE information will begin on the first day of initiation of the study drug.

The NCI Common Terminology Criteria for Adverse Events Version 4 (CTCAE) will be used for toxicity and adverse event reporting. All appropriate treatment areas have access to a copy of the CTCAE version 4.0. A copy of the CTCAE version 4.0 can be downloaded from the CTEP web site (<http://ctep.cancer.gov>).

**Adverse event** is defined according to 21 (CFR 312.32(a)) as any untoward medical occurrence associated with the use of a drug in humans, whether or not considered drug related. An adverse event can also be any unfavorable and unintended diagnosis, symptom, sign (including an abnormal laboratory finding), syndrome, or disease temporally associated with the use of a drug, without any judgment about causality. Adverse event either occurs during the study participation, having been absent at baseline or if present at baseline, appears to worsen.

An abnormal laboratory value will be considered an AE if the laboratory abnormality is characterized by any of the following:

- Results in discontinuation from the study
- Is associated with clinical signs or symptoms
- Requires treatment or any other therapeutic intervention
- Is associated with death or another serious adverse event, including hospitalization
- Is judged by the Investigator to be of significant clinical impact
- If any abnormal laboratory result is considered clinically significant, the investigator will provide details about the action taken with respect to the test drug and about the patient's outcome.

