# 1. OBJECTIVES

## 1.1 Primary Objective

To evaluate the safety and efficacy of topical dexamethasone 0.01% solution used as an oral rinse for prevention of oral chronic graft versus host disease (GVHD).

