### **8.2 Sample Size and Accrual**

07-H-0005

[name].

February 3, 2021

Amendment AA

Using the current overall proportion of clinically significant oral chronic GVHD of 0.25, we note that with 36 patients per arm we would have 80% power to detect the same difference of 30% (15% versus 45%) when testing the difference of proportions at a significance level of 0.05. With amendment R (version date 5-6-2016), we thus propose to reduce the required sample size to 72 subjects. We aim to achieve this new accrual goal within two years and we plan to reassess the futility of protocol if we cannot enroll the expected number of subjects.

**Drop-outs:** In order to maintain appropriate statistical power, subjects who prematurely go off study (i.e. are non-compliant with study requirements or develop oral GVHD in the period between baseline assessments and first dose of study drug) will be replaced. To account for a possible drop-out rate of up to 10%, up to 82 subjects may be accrued. Safety data on drop outs will be included in the safety analysis.

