### 8.5 Data Analyses

This study will be analyzed according to the “intent to treat” principle, that is, all randomized subjects will be included. Subjects not evaluated for endpoints will be considered to have reached the primary endpoint. Every effort will be made to reach and evaluate the subjects at the monthly intervals and at the end of the 3 month intervention period. The differences in proportions of significant oral chronic GVHD will be assessed by a chi-squared test (with continuity correction). Treatment group differences in the severity scores, pain and xerostomia scores, and quality of life scores (OHIP-14) will be assessed using the Wilcoxon test. Adjustments will be made for age and other covariates of interest, such as systemic immunosuppression. Adverse events will be tabulated by severity and treatment assignment. For pediatric subjects, analyses will include growth assessment (growth chart [length for age, weight for age percentiles

and body mass index] for age percentiles) and bone age and the associated z-scores (the number of standard deviations the child's measures [weight, height etc] differ from the population mean).

The intervention period will be 3 months. Should the subject reach the primary endpoint (development of clinically significant oral chronic GVHD), the subject will be asked to participate in end of study assessments and then will go off study. Subjects who did not develop oral chronic GVHD in the intervention phase of the study will be followed for up to 6 months to document late development of oral chronic GVHD. All subjects will be evaluated after 6 months after completion of the intervention phase of the study in the absence of clinical oral GVHD. Final statistical analysis will be performed once all subjects in the sample have completed the study and all records have been collected. We will use stratified analyses to account for effects of systemic immunosuppressive agents and other prognostic factors.

In the event of a protocol violation, the aggregate data will be analyzed with and without those subjects involved in the incident.

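### The by-arm adverse-event table promised in 8.5 is limited by the capture rule in 9.2, without saying so, and may omit oral candidiasis, the complication the protocol expects most

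*Combined protocol and SAP*

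**What the plan says.** Section 1.1 gives the primary objective as "To evaluate the safety and efficacy of topical dexamethasone 0.01% solution used as an oral rinse" for prevention of oral chronic GVHD. Section 8.5 states, with no restriction, "Adverse events will be tabulated by severity and treatment assignment". Section 8.2 adds "Safety data on drop outs will be included in the safety analysis", which settles whose data are used but not which events.

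Section 9.2 sets the capture rule. Because dexamethasone is approved and its toxicity is known, "any observed or volunteered adverse events will not be captured in the database unless (1) the adverse event is previously unknown". Clause (1) continues "not on the label) or more severe than on the label and deemed possibly, probably or definitely related to the study medication". Clause (2) admits an event that "meets the criteria for a severe adverse event". A further sentence says "Adverse events that are complications of the primary transplant protocol and deemed unlikely or unrelated to dexamethasone will not be captured in the database"; those events go to the transplant protocol. On grading, 9.2 says "The NCI Common Terminology Criteria for Adverse Events Version 4 (CTCAE) will be used for toxicity and adverse event reporting", but it gives no grade at which an event counts as severe. Section 9.3 defines *serious* events and limits by attribution which of them are reported on this study. Section 9.4 sends all serious events to the principal investigator.

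On candidiasis, 5.2.1 names candidal overgrowth as the most common complication and puts all subjects on antifungal prophylaxis during the intervention. Section 5.4.1 provides for treatment if it occurs anyway and gives no recording rule. Section 10.3.1 puts its frequency below 5%, with no time window, and calls it easily treatable. It is not among the endpoints in 8.4.

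**The concern.** Read alone, 8.5 promises an ordinary safety table by arm. Read with 9.2, the table can hold only events that passed a filter on label, severity and attribution, and no section says so or brings the excluded events back. The filter works most strongly against mild, expected drug effects, and the protocol's leading expected effect is of that kind. A reader who sees few or no candidiasis cases could conclude that the rinse rarely causes it, when the rule may have kept ordinary cases out of the database.

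**Working it through.** The plan gives no figure for this point, so the first step is to set the passages side by side.

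**What 9.2 lets in**

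- On the label, no worse than labelled, not severe: not captured, whatever the cause.
- On the label, worse than labelled, at least possibly related: captured under clause (1).
- Not on the label, at least possibly related: captured under clause (1).
- Not on the label, judged unrelated or unlikely related, not severe: depends on how clause (1) is read. If the relatedness condition covers the whole clause, the event is out. If it covers only events worse than labelled, the event is in, unless it is a transplant complication, which the separate sentence excludes.
- Severe: captured under clause (2), which has no relatedness condition. The term is undefined there, and 9.3 defines a different one (serious).

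**Candidiasis under this rule.** If it is on the label, non-severe cases no worse than labelled are not captured. If it is not on the label, capture may depend on attribution. Section 2.4.2 says the marketed solution is intended for systemic use, so either is possible.

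**What full capture would show.** Inputs: 36 per arm and 72 in total (8.2); up to 82 accrued, or 41 per arm; a ceiling of 5% (10.3.1). The rates of 3% and 1% are assumed, to show the range.

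- Zero events in an arm, one-sided 95% upper limit = 1 − 0.05^(1/n). For n = 36 this is 7.98%; for n = 41 it is 7.05%.
- 0/36 v 0/36, Newcombe two-sided 95% interval for the difference: −9.64 to +9.64 points.
- Expected cases at 5%: 36 × 0.05 = 1.8 per arm, and 3.6 among 72.
- Chance of at least one case among 72 = 1 − (1 − p)^72. At 5% it is 0.975, at 3% about 0.89, and at 1% about 0.51.
- Power to show an arm difference (Fisher's exact test, two-sided 0.05, 36 per arm): 34% for 5% v 20%, 57% for 5% v 25%, 76% for 5% v 30%. All three rates in the higher arm are assumed.

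The limits above need complete capture. They cannot be applied to cases that the rule keeps out.

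**Time at risk if candidiasis is recorded.** Subjects go off study at the primary endpoint (5.3), so follow-up will differ by arm if the rinse works. Take the 45% and 15% in 8.2 as endpoint rates over the 3-month drug period, with t the mean exit month (assumed) and other exits ignored. Person-months per arm = 36 × [3 − p(3 − t)].

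- t = 1.5 (exits spread evenly): 36 × 2.325 = 83.7 on placebo v 36 × 2.775 = 99.9 on dexamethasone, 19% more on dexamethasone.
- t = 3: 108 v 108, no difference.
- t = 1: 75.6 v 97.2, 29% more.

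If recording ran to month 9 (six months after the drug period, as in 8.5), with no later exits, 3 becomes 9 in the formula. At t = 1.5 this gives 202.5 v 283.5, 40% more on dexamethasone. The range is 29% (t = 3: 226.8 v 291.6) to 44% (t = 1: 194.4 v 280.8).

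**The case against.** The strongest reply is that this is a declared design choice with a stated reason. Section 8.5 can tabulate only what 9.2 captures, so the two can be read together without contradiction, and the caption of an unwritten table cannot be faulted in advance. A barred event might simply have no row, not a misleading zero. Candidiasis may not be on the label at all. Other safety measures are planned: cortisol, dexamethasone level and paediatric growth. Formal power would be low anyway.

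Much of this stands, and it rules out several stronger readings that a reader might infer:

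- *That the filter biases the arm comparison.* The same rule applies in both blinded arms; the loss is of information.
- *That no non-severe case can ever be captured.* A case worse than labelled and at least possibly related still enters, and so would a related case if candidiasis is not on the label.
- *That 9.3 removes unrelated serious events from the database.* It limits what is reported on this study. It does not speak of database entry.
- *That medication records cannot reveal a treated case.* Antimicrobial use is recorded (6.2, 6.3, 6.5), and a newly started, different antifungal could show. The record form is not in the documents, so it is not known whether the indication is collected. With every subject on antifungal prophylaxis, these records are an uncertain substitute.

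The reply does not remove the gap. The stated reason is the known toxicity of the approved drug, yet the précis says the systemic effects of the topical solution are unknown and makes safety part of what the trial evaluates. Nothing in the plan assures that its most expected local effect is counted by arm.

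**Conclusion.** The point holds as a gap in safety information, worth a cheap correction. Followed as written, 9.2 yields a by-arm table that can omit the main expected drug effect, and 8.5 does not tell the reader that the table is selected. Whether ordinary candidiasis is in fact excluded rests on the label, which the documents do not show, and on how clause (1) is read.

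The size of the loss is modest. With full capture the trial could say that an arm with no cases has a true rate below about 8%, and at least one case among 72 subjects would be likely at rates of 3% to 5% and about an even chance at 1%. With the filter it can make no such statement about the excluded cases. It might be inferred that the safety objective cannot be met; the documents do not support that, because the other safety measures remain.

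**What to change.** 1. In 9.2, record oral candidiasis in both arms from first dose to end of study drug, regardless of label or attribution. Use the month 1 and 2 contacts, the month 3 and end-of-study examinations and the antimicrobial records. Make sure each antifungal entry shows prevention or treatment.
2. In 8.5, tabulate candidiasis by randomised arm with time at risk, and state that the rest of the adverse-event table is limited to events meeting the 9.2 capture rule.
3. Reconcile *severe* in 9.2 with *serious* in 9.3, and state whether the relatedness condition in clause (1) covers events not on the label.

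The cost is a few data fields, some data entry and short text changes, with no new visit or test. There are two drawbacks. The month 1 and 2 contacts may be by telephone or email, so some cases would be reported and not examined. Raw counts would also cover unequal time, so the recording window must be stated and time at risk shown; ending the window with study drug keeps that imbalance smaller than recording to month 9.

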## PRÉCIS

Prevention of oral chronic graft versus host disease (GVHD) by topical agents is an attractive strategy because it would potentially avoid the adverse effects associated with systemic immunosuppression. Topically administered dexamethasone solution is a commonly used agent for the prophylaxis of oral inflammatory conditions including GVHD. However, the efficacy and systemic effects of topically administered dexamethasone solution are unknown. We therefore propose this trial designed to evaluate the efficacy and safety of topical dexamethasone solution for prevention of oral chronic GVHD in stem cell transplant recipients.

This pilot phase II study will follow a randomized, double-blind, placebo controlled, parallel group design. Consenting subjects who have undergone hematopoietic stem cell transplantation at the NIH Clinical Center and the surrounding transplant clinics will be randomized 50/50 to receive dexamethasone 0.01% solution or placebo as an oral rinse for 3 months starting 90-100 days post-transplant. Subjects will be evaluated monthly after the start of intervention. Diagnostic and research evaluations will include a complete oral examination, oral mucosal biopsy prior to the beginning of the intervention (day -7) and at the time of development of oral chronic GVHD or at the completion of intervention in the absence of clinical GVHD. We will measure serum dexamethasone levels and perform short cosyntropin (ACTH stimulation) test at the end of the 3 months of intervention or onset of clinically significant GVHD.

The primary objective of the study is to evaluate the safety and efficacy of topical dexamethasone 0.01% solution used as an oral rinse for prevention of oral chronic GVHD. Our primary endpoint will be the proportion of subjects that develop clinically significant (severity score 3 or higher) oral chronic GVHD after three months.

Secondary objectives will include the impact of oral chronic GVHD on the quality of life, characterization of the changes in tissue and salivary biomarkers associated with development of oral graft versus host disease, and measures of the effects of topical dexamethasone on hypothalamo-pituitary-adrenal axis. Secondary outcomes will include oral cavity specific quality of life as measured by OHIP-14 questionnaire, oral discomfort levels, improvement in general quality of life scores, and severity of oral chronic GVHD as measured by the site-specific GVHD scoring system.

---

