## **4. ELIGIBILITY ASSESSMENT**

### **4.1 Inclusion Criteria**

- 4.1.1 History of allogeneic hematopoietic stem cell transplantation within 60-90 days of enrollment.
- 4.1.2 Age 12 or older.
- 4.1.3 Ability to rinse and expectorate study medication rather than swallow it.
- 4.1.4 Ability and willingness to come to Clinical Center for follow-up appointments and at the time of development of symptoms/signs suggestive of oral GVHD.

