### **4.3 Subject Registration and Prophylactic Treatment Randomization**

Subjects will be recruited from NIH Clinical Center and the surrounding transplant clinics. After confirmation of eligibility and execution of an informed consent, the Principal Investigator or the research nurse will notify the pharmacy of the subject's enrollment and the pharmacy will randomize the subject to therapy. Both investigators and subjects will be blinded to the group assignment until the completion of the study. Assignment of treatment will be done using a block randomization scheme with the assignment probability remaining fixed over the course of the trial. Construction of the randomization schedule is done by pharmacy using a table of random numbers. Subjects will be stratified by the type of conditioning (myeloablative vs. non-myeloablative) to ensure comparable groups.

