## **6. CLINICAL MONITORING AND ASSESSMENTS**

### **6.1 Pre-study Evaluation and Assessments**

#### **6.1.1 Eligibility assessment**

Subjects will be screened for eligibility between days 60 and 90 post transplant using the following assessments which are done under the subject's parent transplant protocol or the NHLBI screening protocol 1997-H-0041:

- Review of medical history
- Review of concomitant meds
- Blood pressure
- Complete oral examination
- Complete blood count (CBC with diff) –done concurrently with post transplant monitoring
- Consent if eligible and randomization

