### **9.3 Serious Adverse Events**

A serious adverse event is any untoward medical occurrence that:

- results in death
- is life-threatening, requires or prolongs hospitalization
- causes persistent or significant disability/incapacity
- results in congenital anomalies/birth defects
- or in the opinion of the investigators represents other significant hazards or potentially serious harm to research subjects or others.

Only those SAEs that are determined possibly, probably or definitely related to this protocol will be reported on this ancillary study. Those determined possibly, probably or definitely to post transplant complications will be reported on the transplant protocol.

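### Sections 9.2–9.4 leave transplant-attributed events to a transplant protocol that subjects from surrounding clinics need not be on, so those events have no assured place in this trial's data

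*Combined protocol and SAP*

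**What the plan says.** **Who can enter.** The Précis describes subjects who have undergone "hematopoietic stem cell transplantation at the NIH Clinical Center and the surrounding transplant clinics will be randomized 50/50". Section 4.3 repeats this: "Subjects will be recruited from NIH Clinical Center and the surrounding transplant clinics". Section 4.4 sets out letters to physicians and a flyer for those clinics, and section 10.1 names the same sources. The transplant criterion in 4.1 is "History of allogeneic hematopoietic stem cell transplantation within 60-90 days of enrollment". Nothing in 4.1 or 4.2 asks for enrolment on a transplant protocol. Section 6.1.1 has the screening assessments "done under the subject's parent transplant protocol or the NHLBI screening protocol 1997-H-0041".

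**Which events are kept.** Under 9.2, "any observed or volunteered adverse events will not be captured in the database unless" one of two conditions is met: the event is unlabelled or worse than labelled and at least possibly related to study medication, or it counts as severe. A further rule in 9.2 concerns events that are complications of the primary transplant protocol and are also considered unlikely or not related to dexamethasone. These "will not be captured in the database for this protocol, but will be collected and reported in the transplant protocol".

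**Serious events.** Section 9.3 limits SAE reporting on this study to events at least possibly related to it, and adds: "Those determined possibly, probably or definitely to post transplant complications will be reported on the transplant protocol". Section 9.4 has all SAEs reported to the principal investigator, without a relatedness condition. The DSMB receives SAEs considered at least possibly related.

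**What the data are for.** Safety is part of the primary objective (1.1, 8.3), and 8.5 tabulates adverse events by severity and treatment arm.

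**The concern.** The safety sections assume that a second study collects what this one leaves out. The recruitment and eligibility sections do not guarantee that this second study exists for every subject, or that it is one whose data this trial can obtain.

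The stake is the by-arm safety comparison. Section 2.4.1 lists life-threatening infections among the harms of long-term systemic immunosuppression and associates systemic corticosteroids with infections. Section 2.5 says that absorption of the expectorated rinse has not been studied. The rinse is topical, so the risk may well be small, but the trial is meant to find that out. An infection after transplant can readily be put down to the transplant. Because investigators are blinded, attribution should not by itself favour one arm. It does, however, remove the very events that would reveal an excess nobody suspected. The usual protection is to compare serious events by arm whatever their attribution, and that requires the events to be in an accessible dataset.

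**Working it through.** The plan gives no figure on this point and no arithmetic applies. The check follows each type of event through 9.2–9.4 for each type of subject that the recruitment text allows.

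| Subject | Event | This trial's database or reports | DSMB review under 9.4 | Other destination |
|---|---|---|---|---|
| Any | SAE at least possibly related to this study | Yes (9.3) | Yes | – |
| On an NIH transplant protocol | Transplant complication, unlikely or not related to dexamethasone | No | No | That protocol |
| On an outside clinic's own protocol | Same | No | No | That protocol; no data flow to this trial is described |
| On no transplant protocol | Same | No, if the 9.2 rule is applied | No | None named |

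In the last three rows an SAE is still notified to the principal investigator. Notification is not database entry, and 9.3 keeps such an SAE off this study's reports.

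1. *Can the last two rows occur?* The Précis, 4.3, 4.4 and 10.1 plan for subjects from surrounding clinics, and 4.1–4.2 would admit them with no parent protocol. In 6.1.1 the screening protocol is an alternative to "the parent protocol" for screening assessments. That is compatible with a subject having no parent protocol but does not establish it.

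2. *Does the 9.2 exclusion apply without a primary transplant protocol?* Read narrowly, such a subject cannot have a complication of a protocol they are not on. Severe events would then be captured by the second condition in 9.2. Non-severe events would still be left out unless they met the first condition. The text does not choose between the readings, and 9.3 and 9.4 contain no matching exception.

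3. *Does anything else say where these events go?* Nothing in the documents provides for a subject without an NIH transplant protocol, or for obtaining adverse event data from an outside clinic's study.

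**The case against.** The strongest reply is that co-enrolment is presupposed throughout. Section 5.2.2 refers to the subject's primary transplant protocol, 10.4.2 describes post-transplant subjects who co-enrol, and 9.3 and 9.4 call this an ancillary study. If everyone is in fact co-enrolled, only the outside-protocol row of the table could remain. This shows what the authors had in mind. It does not turn co-enrolment into an eligibility criterion, and it sits uneasily with recruitment from other clinics.

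A second reply is that safety information still reaches the team. All SAEs go to the principal investigator (9.4). Contacts at 1 and 2 months ask about adverse effects and review available laboratory results (6.2). Clinic visits follow (6.3, 6.5). Safety data on drop-outs enter the safety analysis (8.2), and parent-protocol hand x-rays are reviewed where available (6.1.2, 6.3). This stands, and it limits the point.

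It also rules out two stronger inferences that a reader might draw. One is that transplant-attributed events in outside subjects are recorded nowhere. For SAEs, 9.4 contradicts that, and clinical records or a local protocol may hold others. The second is that a later by-arm check would be impossible. It would not be assured, because no section requires these events to be entered or retrieved, but the documents do not show that it could not be done. Nor is every transplant-related event excluded: the 9.2 rule has two parts, and an SAE considered possibly related to the study remains reportable on it.

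**Conclusion.** The point holds as a gap between sections. Followed as written, 9.2–9.4 keep transplant complications assessed as unlikely or not related to dexamethasone off this study. For a subject without a transplant protocol, or on an outside clinic's own, no assured alternative is given that this trial or its DSMB can use. For SAEs the gap concerns database entry and DSMB review, not notification.

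The size cannot be derived from the documents. They do not give the share of outside subjects or say how many lack a parent protocol; the number could be zero. A reader might apply an assumed share of 10% to 40% to the accrual ceiling of 82 (0.10 × 82 = 8.2; 0.40 × 82 = 32.8) and conclude that about 8 to 33 subjects would have no record of such events. The documents do not support that. The share has no source, the result counts subjects and not lost events, and it treats every outside subject as having no protocol and no record.

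The conclusion rests on two assumptions: that surrounding-clinic recruitment is real, and that the second rule in 9.2 is applied to these subjects. It merits an amendment because safety is part of the primary objective and the remedy is cheap.

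**What to change.** Amend 9.2–9.4 so that every SAE already notified to the principal investigator, from first dose to end of study, is entered in this protocol's database with its attribution and summarised by arm for the DSMB. Use the term serious as defined in 9.3, since the second condition in 9.2 says severe.

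Preferably apply this to all subjects. Restricting it to outside subjects would make SAE capture differ by recruitment source, with NIH subjects still filtered by attribution. At minimum, apply it to any subject not on an NIH transplant protocol. Record recruitment source and parent protocol, if any, at registration. State also where non-serious transplant-attributed events are held for subjects without an NIH transplant protocol, or that they are not collected.

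The cost is a wording change and modest data entry, since the investigator already receives the reports and the contacts and visits already exist. The downside is more unrelated events in the tabulation; showing attribution alongside each event keeps it readable. No treatment, visit or endpoint changes.
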